3. OBJECTIVES

Primary Objective(s):

To evaluate the memory response, as measured by anti-LPS *S. sonnei* serum IgG, 7 days after vaccination with a booster dose of GVGH *S. sonnei* 1790GAHB vaccine in individuals who had undetectable antibody titers at baseline in H03_01TP, approximately two to three years after the third vaccine dose, compared to administration of 1 single vaccine dose to placebo recipients with undetectable antibody titers at baseline in H03_01TP or naïve subjects who were not part of H03_01TP study.

Secondary Objective(s):

1) Safety:

- a. To evaluate the safety profile of one dose of GVGH *S. sonnei* 1790GAHB vaccine in subjects who previously received three vaccinations with 1790GAHB and in subjects receiving one dose 1790GAHB for the first time (either placebo recipients in H03_01TP or naïve subjects who were not part of H03_01TP study).

- b. To evaluate the safety profile of one dose of GVGH *S. sonnei* 1790GAHB vaccine in subjects receiving one dose 1790GAHB for the first time and having detectable antibodies at baseline of the extension trial.

2) Immunogenicity:

- a. To evaluate the immunogenicity profile 7, 14, 28 and 84 days after vaccination with one dose of GVGH *S. sonnei* 1790GAHB vaccine in subjects with undetectable antibody titers at baseline who previously received three vaccinations of GVGH *S. sonnei* 1790GAHB vaccine in H03_01TP and in placebo recipients with undetectable antibody titers at baseline in H03_01TP or naïve subjects with undetectable antibody titers at baseline who were not part of H03_01TP study.
- b. To evaluate the immunogenicity profile of one dose of GVGH *S. sonnei* 1790GAHB vaccine in naïve subjects receiving one dose 1790GAHB for the first time and having detectable antibodies at baseline of the extension trial.
- c. To evaluate the persistence of anti-LPS *S. sonnei* serum IgG antibody titers approximately two to three years after the third vaccination with 1790GAHB.

3) Exploratory:

Other immunological assays might be performed to further characterize the immune response to the study vaccine including serum secretory IgA.

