2.2 Secondary Objective(s)

Secondary Safety Objective(s)

- a. To evaluate the safety profile of one dose of GVGH *S. sonnei* 1790GAHB vaccine in subjects who previously received three vaccinations with 1790GAHB and in subjects receiving one dose 1790GAHB for the first time (either placebo recipients in H03_01TP or naïve subjects who were not part of H03_01TP study).
- b. To evaluate the safety profile of one dose of GVGH *S. sonnei* 1790GAHB vaccine in subjects receiving one dose 1790GAHB for the first time and having detectable antibodies at baseline of the extension trial. **Secondary Efficacy Objective(s)**

This study has no secondary efficacy objectives.

Secondary Immunogenicity Objective(s)

- a. To evaluate the immunogenicity profile 7, 14, 28 and 84 days after vaccination with one dose of GVGH *S. sonnei* 1790GAHB in subjects with undetectable antibody titers at baseline who previously received three vaccinations of 1790GAHB in H03_01TP and in placebo recipients with undetectable antibody titers at baseline in H03_01TP or naïve subjects who were not part of H03_01TP study.
- b. To evaluate the immunogenicity profile of one dose of GVGH *S. sonnei* 1790GAHB vaccine in subjects receiving one dose 1790GAHB for the first time and having detectable antibodies at baseline of the extension trial.
- c. To evaluate the persistence of anti-LPS *S. sonnei* serum IgG antibody titers approximately two to three years after the third vaccination with 1790GAHB.

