4. SELECTION OF STUDY POPULATION

4.1 Inclusion Criteria

In order to participate in this study, all subjects must meet ALL of the inclusion criteria described. Are included:

1. Males and females, aged 22 to 50 years, who were previously vaccinated, with either vaccine (3 doses) or placebo, in H03_01TP and who had undetectable antibody titers at baseline, or Males and females, aged 22 to 50 years, who were not part of H03_01TP.
2. Individuals who, after the nature of the study has been explained to them, and prior to any protocol specific procedures being performed, have given written consent according to local regulatory requirements.
3. Individuals in good health as determined by the outcome of medical history, physical examination, hematological blood tests and clinical judgment of the investigator.
4. If women of child-bearing potential, have a negative urinary pregnancy test prior study vaccination and willingness to use acceptable birth control measures for the entire study duration.
5. Individuals affiliated to a social security regimen.

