2. STUDY DESIGN

This is an open label, non-randomized, single center, Phase 1 clinical trial. The study includes a screening visit (performed at study Days -21 to -1), one clinical visit with vaccination (performed at study Day 1), 4 clinical visits (performed 7, 14, 28 and 84 days after vaccination), and 2 phone calls (performed 2 and 6 days after the vaccination).

Table 2-1 H03_01TP Study Design

| H03_01TP | H03_01E1TP | | | |
|---------------|---------------|-----------------------|--------------|---------------|
| | | | | |
| Vaccine group | No. subjects* | New enrolled subjects | No. subjects | Vaccine group |

| | | | |
|-------------------|----|----------------|------------------|
| 1790GAHB – 1 µg** | 5 | 5 | 1790GAHB – 25 µg |
| 1790GAHB – 5 µg | 4 | 4 | 1790GAHB – 25 µg |
| 1790GAHB – 25 µg | 2 | 2 | 1790GAHB – 25 µg |
| 1790GAHB – 50 µg | 4 | 4 | 1790GAHB – 25 µg |
| 1790GAHB – 100 µg | 5 | 5 | 1790GAHB – 25 µg |
| Placebo | 4 | 4 | 1790GAHB – 25 µg |
| Total H03_01TP | 24 | Naïve subjects | 26 |
| Grand total | | | 50 |

*only subjects with undetectable antibodies at baseline.

** µg of total protein

Up to 50 subjects will be enrolled into this trial. Up to 24 subjects are eligible from the parent H03_01TP trial. With respect to naïve subjects who were not part of H03_01TP study, considering that in the original H03_01TP population 50% of subjects did not have detectable antibodies at baseline, with 26 subjects, approximately 13 subjects should not have detectable antibodies. This number combined with that of placebo recipients in H03_01TP should be sufficient to allow a balanced contribution of previously unvaccinated and vaccinated subjects in the extension trial.

Blood Draw Procedure

A blood draw will be obtained for hematological and serological (HIV, hepatitis B and C) tests for subjects who were part of the parent trial (H03_01TP). For naïve subjects a blood draw will be obtained for the same hematological and serological tests mentioned above and in addition for HLA-B27 testing as part of the initial screening.

One additional blood draw for hematological tests will be obtained at 7 days (Visit 2) and 84 days (Visit 5) after vaccination.

Each subject will have blood drawn for immunological studies before and 7, 14, 28 and 84 days after vaccination. For the purpose of creating a standard reference serum for the serological assay, an additional blood sample will be collected at 28 days after vaccination (Visit 4).

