6.4.2. Additional considerations

The percentage of subjects with seroresponse by titer at baseline and with post vaccination antibody level ≥ 121 IgG units

Pearson CIs will be computed by vaccine group at each visit and associated two-sided 95% Clopper-

Unadjusted GMCs and associated two-sided 95% CIs will be computed for each group at each visit. For each vaccine group, unadjusted GMCs and their 95% CIs will be obtained by exponentiating (base 10) the least square means and the lower and upper limits of the 95% CIs of the log-transformed titers or concentrations (base 10).

Titers below the limit of detection will be set to half that limit for the purposes of analysis. Missing values of immunogenicity will be excluded from analyses (i.e. complete-case analysis) since they are considered missing completely at random, i.e. not informative and with no impact on inferences

The immunogenicity tables will show some or all of the following subgroups. See mock up tables.

Shigella group: subjects from parent study H03_01TP who previously received three vaccinations with 1790GAHB regardless of the total protein amount.

Placebo group: subjects from parent study H03_01TP who previously received vaccinations with Placebo.

Naïve group: naïve subjects enrolled in H03_01E1TP.

Pla+Naïve: subjects from parent study H03_01TP who previously received vaccinations with Placebo plus naïve subjects enrolled in H03_01E1TP

Subjects with detectable antibodies at baseline (i.e. with antibodies at baseline \geq Lower Limit of quantification, LLOQ)

Subjects without detectable antibodies at baseline (i.e. with antibodies at baseline $<$ LLOQ)

Note that in Shigella and Placebo groups the LLOQ was assessed at the baseline of the parent study H03_01TP, while in Naïve group the LLOQ will be assessed at baseline of extended study H03_01TP.

1MG_SHI, 5MG_SHI, 25MG_SHI, 50MG_SHI, 100_MG_SHI: subjects from parent study H03_01TP who previously received vaccinations with GVGH *Shigella sonnei* 1790GAHB vaccine containing 1 mcg, 5 mcg, 25 mcg, 50 mcg, 100 mcg of total protein amount respectively.

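### The primary Day-7 comparison allows antibody-positive naïve subjects into the first-dose comparator (about 13 of 30), although the sizing text and SAP objective 2a assume antibody-negative comparators

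*SAP*

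**What the plan says.** **Primary objective.** SAP section 3 repeats Protocol 2.1. The Day-7 response in boosted subjects with undetectable antibody at the parent-study baseline is set against "placebo recipients with undetectable antibody titers at baseline in H03_01TP or naïve subjects who were not part of H03_01TP study". The antibody condition attaches to the placebo recipients only.

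**Eligibility.** For new recruits, criterion 1 in Protocol 4.1 asks only for "Males and females, aged 22 to 50 years, who were not part of H03_01TP". It has no antibody condition.

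**Sizing.** SAP section 2 expects that "with 26 subjects, approximately 13 subjects should not have detectable antibodies". It adds that number to the placebo recipients to argue for balance with the previously vaccinated subjects.

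**Secondary objective 2a.** The protocol refers to the immunogenicity profile "in placebo recipients with undetectable antibody titers at baseline in H03_01TP or naïve subjects who were not part of H03_01TP study". The SAP limits the last group to "naïve subjects with undetectable antibody titers at baseline who were not part of H03_01TP study". SAP section 9 reports no change from the planned analyses.

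**Analysis text.** SAP 6.4.2 states that "The immunogenicity tables will show some or all of the following subgroups". The list includes Pla+Naïve with no antibody limit and, separately, "Subjects without detectable antibodies at baseline". No entry is tied to the primary objective. The reverse cumulative curves in SAP 6.4.1 use Shigella and Placebo+Naïve.

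**Safety.** Objective 1b concerns first-dose subjects with detectable antibody at the extension baseline. SAP 6.5.2 names Shigella, Pla+Naïve and Total.

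**The concern.** The study asks whether three earlier doses left immunological memory in adults who started without detectable antibody. The natural comparison is with first-dose subjects who also start without it. An antibody-positive naïve subject has probably met the antigen before, so a fast response in that subject may itself be recall.

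As worded, the primary Day-7 description can be read in two ways: against about 30 first-dose subjects of mixed status, or against about 17 antibody-negative ones. The parent-study account in the protocol synopsis gives a direction. At 25 to 100 µg, one-month medians stood well above 121 EU/mL in subjects detectable at baseline, and above it, without that emphasis, in undetectable subjects. If Day 7 follows the same direction, pooling raises the first-dose GMC and makes the booster response look less distinct. The trial is open label and the analysis is descriptive, so fixing the main contrast in writing is the main guard against choosing it after the results are seen.

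**Working it through.** **Inputs.** From the study design table (SAP section 2, Protocol synopsis): vaccinated parent subjects 5 + 4 + 2 + 4 + 5 = 20; placebo 4; naïve 26; total 50. Share undetectable: 50%, from the sizing text.

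**The plan's own figure.** 26 × 0.50 = 13 antibody-negative naïve subjects, as stated.

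**The two comparators, at full enrolment.**

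| Reading | First-dose subjects | Antibody-positive | Boosted |
|---|---|---|---|
| Primary objective as worded | 4 + 26 = 30 | 26 − 13 = 13 (13/30 = 43%) | 20 |
| Sizing text and SAP 2a | 4 + 13 = 17 | 0 | 20 |

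Placebo recipients count as negative here by parent-study baseline, as SAP 6.4.2 specifies.

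**Uncertainty in the 13.** With the rate fixed at 0.5, the central 95% range of Binomial(26, 0.5) is 8 to 18 positives. The rate itself comes from only 50 parent subjects. Taking 25 of 50 (an assumption) with a Jeffreys prior gives a Beta(25.5, 25.5) distribution for the rate, and the beta-binomial range widens to 7 to 19. That is 7/30 = 23% to 19/30 = 63% of the pool, leaving 30 − 19 = 11 to 30 − 7 = 23 antibody-negative comparators.

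**Effect on the GMC (illustration only).** If positives had a Day-7 GMC *k* times that of negatives, the pooled GMC would be inflated by *k*^(13/30): 1.35 for *k* = 2 and 1.61 for *k* = 3. The booster-to-first-dose ratio would shrink by the same factor. The documents give no Day-7 value of *k*.

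**Precision cost of restricting.** The half-width of a log-scale 95% CI in SD units is t(0.975, n−1)/√n: 0.3734 at n = 30 and 0.5142 at n = 17, a ratio of 1.38 at equal SD. If the strata differ, pooling also inflates the SD. With an assumed within-stratum log10 SD of 0.5 and a 3-fold stratum ratio:

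- pooled variance = 0.25 + (13/30)(17/30)(log10 3)² = 0.25 + 0.056 = 0.306, so SD = 0.553;
- ratio = 1.38 × 0.5/0.553 = 1.24.

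**Objective 1b.** About 13 naïve subjects plus 0 to 4 placebo recipients who might be detectable at Day 1 gives 13 to 17.

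**SAP wording against the protocol.**

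- 2a: antibody limit added for naïve subjects.
- 2b: narrowed to naïve subjects.
- Primary endpoint: seven days added in SAP section 4; Protocol 8.1.1.3 gives no time point.
- SAP section 9 records none of these.

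**The case against.** The strongest reply is that the antibody-negative comparison is already planned. SAP 2a includes Day 7 and limits all three groups to undetectable baseline, secondary endpoint a is the GMC at that visit, and 6.4.2 defines both antibody strata. This stands. A reader might infer that the SAP offers no like-for-like Day-7 description, and that would be wrong. What stays open is which description answers the primary objective, and the curves still use the mixed pool.

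Second, nothing is tested, there are no success criteria, and all analyses are descriptive. This also stands: the point concerns how the memory response is read, not a false-positive rate. The SAP also reproduces the protocol's primary objective faithfully, so the gap starts in the protocol.

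Third, the parent data are one-month medians pooled over three doses. They support a direction only. A reader might conclude that pooling will hide a memory response by a known amount; the documents do not support that.

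Fourth, a reader might infer that objective 1b will go unreported. SAP 6.5.2 and section 10 point to mock tables and a contents list that were not available. Annex 3 says standard mock tables will be used, which makes a dedicated column less likely but does not exclude one, and by-subject adverse event listings are planned.

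Finally, 6.4.2 says "while in Naïve group the LLOQ will be assessed at baseline of extended study H03_01TP". It would be tempting to call the naïve baseline undefined. The same section places naïve subjects in H03_01E1TP, so this is a slip in the study number.

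**Conclusion.** The concern holds in a limited form. The primary objective leaves the antibody status of naïve comparators open. Taken as written, about 43% of the first-dose group would be antibody-positive (predictive range 23% to 63%), whereas the sizing text and SAP 2a point to about 17 antibody-negative subjects against 20 boosted. These counts assume full enrolment, the plan's 50% rate and, for the range, 25 of 50 in the parent study. The likely effect is a higher first-dose GMC and a narrower contrast, of unknown size at Day 7. It is worth correcting because the correction is cheap and bears on the study's main question.

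The absence of a named safety group for objective 1b is a separate point, held with moderate confidence because the table shells were not available.

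**What to change.** In the SAP:

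1. Name Shigella versus antibody-negative Pla+Naïve as the Day-7 GMC description that answers the primary objective. Use the 6.4.2 reference baselines: parent study for Shigella and Placebo, extension Day 1 for Naïve. Correct the study number in that rule.
2. Use the same groups for the reverse cumulative curves, and keep pooled Pla+Naïve as supportive.
3. State that a placebo recipient detectable at Day 1 stays in the primary comparator by parent baseline but also counts for objective 1b. Flag any such subject, or show the result without them.
4. Record the wording changes to 2a, 2b and the primary endpoint in section 9, together with this clarification.
5. Add a safety-table column for first-dose subjects with detectable Day-1 antibody, or cite the existing entry in the table contents list.

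**Cost.** Text edits, one safety column and a check of the contents list. No new samples are needed, since Day-1 ELISA is planned for everyone. The comparator falls from about 30 to about 17, so its log-scale CI is about 1.38 times wider at equal SD and less if pooling inflates the SD (1.24 in the example above). A protocol amendment may be needed if the sponsor regards this as changing the objective and not merely clarifying it.

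### The SAP narrows immunogenicity objective 2b to naïve subjects and fixes placebo recipients' serostatus at the parent baseline, so none can enter the detectable stratum, and the change is not declared

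*SAP*

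**What the plan says.** **Protocol 2.2, secondary immunogenicity objective b.** The profile of one dose is to be evaluated "in subjects receiving one dose 1790GAHB for the first time and having detectable antibodies at baseline of the extension trial". Safety objective a of the same section spells out who first-dose subjects are: "either placebo recipients in H03_01TP or naïve subjects who were not part of H03_01TP study".

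**SAP section 3, immunogenicity objective b.** The population becomes "in naïve subjects receiving one dose 1790GAHB for the first time and having detectable antibodies at baseline of the extension trial". In the same list, SAP safety objective b keeps the protocol's wider wording.

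**SAP 6.4.2, subgroups.** Placebo recipients and new enrollees are distinct groups, the latter defined by "Naïve group: naïve subjects enrolled in H03_01E1TP". Detectable and undetectable subgroups are set by the LLOQ at baseline, with two reference times. The parent-trial groups follow one rule: "Note that in Shigella and Placebo groups the LLOQ was assessed at the baseline of the parent study H03_01TP". New enrollees are handled differently, on a sample from the present trial: "while in Naïve group the LLOQ will be assessed at baseline of extended study".

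**Protocol 4.1, inclusion criterion 1.** Parent-trial subjects enter only if they were vaccinated "in H03_01TP and who had undetectable antibody titers at baseline".

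**SAP section 9.** Changes from planned analyses are given as not applicable. SAP section 1 shows that the SAP was written against protocol Version 2, which carries the wider objective b.

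**The concern.** The protocol asks how people given their first dose respond when they already carry antibody on the day of that dose. A former placebo recipient who became detectable between the trials belongs to that question. The SAP removes such a person twice: once by adding the word naïve to the objective, and again by reading serostatus from a sample on which the answer was fixed by eligibility.

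Three things are at stake.

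- The reported 2b population may differ from the one in the protocol, with nothing in the SAP to tell the reader so.
- Safety objective b and immunogenicity objective b now describe different people, without a stated reason.
- The labels can clash within one table. Protocol 8.4.2.3.3 and SAP 6.4.1 compute GMRs against Day 1 of the extension in every group, so a subject labelled undetectable at baseline could contribute a detectable baseline to the ratio.

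**Working it through.** **1. Counts in the plan (SAP Table 2-1).** Parent-trial subjects: 5 + 4 + 2 + 4 + 5 + 4 = 24, of whom 20 were primed and 4 received placebo. With 26 naïve subjects the total is 24 + 26 = 50. At the plan's 50%, 26 × 0.5 = 13 naïve subjects are expected to be undetectable and 13 detectable. All of these match the documents.

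**2. Following one placebo recipient through the two texts.** Suppose the Day 1 sample is detectable.

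| Step | Protocol 2.2 b | SAP |
|---|---|---|
| Receiving a first dose? | Yes | Yes |
| In the objective's population? | Yes | No, naïve only (section 3) |
| Sample that sets serostatus | Extension baseline | Parent baseline (6.4.2) |
| Serostatus | Detectable | Undetectable, by inclusion criterion 1 |
| Counted under 2b? | Yes | Never |

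**3. Age of the sample used.** Parent doses were one month apart, so the third came about 2 months after baseline. The extension dose follows 24 to 36 months later. The parent baseline is therefore about 24 + 2 = 26 to 36 + 2 = 38 months old at Day 1.

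**4. Effect on group sizes.** Let k be the number of the 4 placebo recipients detectable at Day 1. Under the protocol's objective b the detectable first-dose group is 13 + k, that is 13 to 17. Under the SAP it is 13 whatever k is. At most 4 subjects are omitted, or 4/17 = 24% of the group at k = 4; at k = 1 it is 1/14 = 7%.

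**5. How likely is k ≥ 1?** The documents give no rate. With an assumed probability q per subject and independence, P(k ≥ 1) = 1 − (1 − q)^4:

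| Assumed q | P(k ≥ 1) | Expected k = 4q |
|---|---|---|
| 0.05 | 19% | 0.2 |
| 0.10 | 34% | 0.4 |
| 0.20 | 59% | 0.8 |
| 0.30 | 76% | 1.2 |

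These figures show only that the case need not be remote. Exclusions 21 and 22 (known or suspected *S. sonnei* disease, contact with a confirmed case) should lower q. They do not make detectable antibody impossible: they apply to the naïve recruits too, and the plan still expects about half of those to be detectable.

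**6. Is the information available?** Yes. Protocol 3.1 and Table 4 schedule anti-LPS IgG at Day 1, before vaccination, in all 50 subjects.

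**The case against.** **The narrowing may be deliberate.** SAP objective 2a also adds a requirement, absent from the protocol's 2a, that naïve subjects be undetectable. The two edits together give a clean split: all placebo recipients in 2a, naïve subjects divided between 2a and 2b. Under the protocol's wording a placebo recipient detectable at Day 1 would fall in both. A tidy split is a reasonable aim, but it changes an objective, and section 9 is where that should be said.

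**Part of it would show anyway.** SAP 6.4.2 defines Placebo as its own group, SAP 6.4.1 gives GMCs at each sampled time point, and reverse cumulative curves are planned per visit for Placebo plus Naïve. One raised Day 1 value among four would move that group's baseline GMC. This stands in part: the value might be visible, but it would not be counted under 2b. The tables show some or all subgroups, and the mock tables are not in the text, so the final layout cannot be judged.

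**A stronger reading that does not hold.** A reader might infer that the SAP puts exposed placebo recipients wrongly among the undetectable comparators, raises their Day 7 GMC and so hides a memory response. The documents do not support this, for four reasons.

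- Protocol 2.1 and objective 2a in 2.2 define placebo recipients by undetectable titers at the parent baseline. Using that sample there is the plan, not a departure.
- Moving only Placebo to Day 1 while primed subjects stay on the parent baseline would create an asymmetry, since both groups lived through the same interval.
- SAP 6.4.1 plans within-group estimates, without hypothesis or success criterion. No between-group contrast is specified for this to bias.
- The size cannot be sourced. The protocol background calls detectable high-dose subjects far higher relative to 121 EU/mL, not relative to undetectable subjects, and the first post-dose sample in the parent trial was at 28 days, so there is no Day 7 figure. For scale only: one subject at an assumed 3, 10 or 30 times the others would multiply the GMC of 4 + 13 = 17 undetectable first-dose subjects by 3^(1/17) = 1.07, 10^(1/17) = 1.15 or 30^(1/17) = 1.22.

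**Conclusion.** The concern holds for objective 2b. The SAP's objective wording and its serostatus rule each keep parent-trial placebo recipients out of the detectable first-dose stratum, the protocol puts them in it, and SAP section 9 declares no change. SAP safety objective b, left at the wider wording, shows the inconsistency within the SAP itself.

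The size is small: at most 4 subjects, possibly none, in a descriptive secondary objective. The conclusion rests on the texts and on the planned count of 4. It does not rest on the assumed probabilities or fold differences, which are illustrative. It does not extend to the primary objective or objective 2a.

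**What to change.** 1. In SAP section 3, restore the protocol wording of immunogenicity objective b.
2. In SAP 6.4.2, state that for objective b (safety and immunogenicity) all first-dose subjects, Placebo and Naïve, are classified as detectable or undetectable on the H03_01E1TP Day 1 sample. SAP 6.5.2 lists no serostatus subgroup, so it needs a cross-reference to this rule. Correct the study number in the same note, where the extension is labelled H03_01TP.
3. Keep the parent-baseline definition of placebo recipients for the primary objective and objective 2a, and say that a placebo recipient detectable at Day 1 appears under both 2a and 2b.
4. List the Day 1 concentrations of the four placebo recipients. A sensitivity row for the primary summary, excluding any who are detectable at Day 1, is optional.
5. If the narrowing is intended, leave the wording but declare and justify it in section 9.

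The cost is a few SAP sentences, one short listing and at most one extra row. No new sample or assay is needed.
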